**Aim 3: To examine the effects of neurofeedback-guided motor imagery training on motor function.**

We will measure the severity of motor dysfunction using clinical rating scales and administer standard motor function tests (e.g., timed up and go, five times sitting-to-standing) to measure movement speed and vigor in PD-neurofeedback and PD-control groups. These measurements will be performed at baseline and post-training. *Hypothesis: There will be significant improvement in motor function in the PD-neurofeedback compared with the PD-control group post-training.*

This project has potential for direct clinical significance for patients with PD: 1) Interventions such as deep brain stimulation exert their effect by altering the abnormal activity of targeted brain circuits underlying PD pathology. fMRI-based neurofeedback training offers an unprecedented opportunity to have a similar effect noninvasively. 2) The mental strategies that were successfully and reliably used during neurofeedback could be practiced off-line. Therefore, neurofeedback has the potential to be implemented as a personalized treatment modality. 3) It could also be incorporated into rehabilitation and exercise programs as an adjunct treatment modality.

**Rationale for Additional fMRI Experiments:** 1) Our findings have shown that despite engaging different brain networks specific to imagery type (i.e., motor versus visual), subjects in both PD-neurofeedback and PD-control groups improved their motor function comparably (Tinaz et al., 2022). This suggests that there may be a "shared" brain network subserving both motor and visual imagery and mediating the motor response. To test this hypothesis further, we plan on using a hybrid mental imagery of everyday task performance in the scanner that will include both motor and visual features. The results of this experiment will also inform the choice of off-line imagery practice that can potentially yield most benefits. 2) It is also important to establish to what extent mental imagery of everyday task performance is equivalent to observation of the actual task performance in terms of brain networks. If the brain networks involved in these tasks overlap significantly, this will further support the use of mental imagery as a mental training tool.

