**3. Research Strategy for the Exploratory Aims:**

**Subjects:** We plan on recruiting 15 new subjects with PD. Subjects who are interested in participating in the study will undergo medical history and MRI screening for eligibility in-person or via phone/email. The standard MRI Safety Questionnaire that was developed at the MRRC will be used. All experimental procedures will be completed in one research visit. Subjects will continue to take their PD medications as scheduled throughout the research visit.

**Clinical Evaluation:** [name] will perform an initial physical and neurological examination on all subjects. The diagnosis of idiopathic PD will be made according to the UK Brain Bank diagnostic criteria (Hughes et al., 1992). The Movement Disorders Society-Unified Parkinson's Disease Rating Scale (MDS-UPDRS) (Goetz et al., 2008) and Hoehn & Yahr staging (Hoehn and Yahr, 1998) will be used to determine disease severity and stage of PD subjects. The Montreal Cognitive Assessment test will be administered to rule out dementia (Nasreddine et al., 2005). Self-evaluation questionnaires will be administered including: Beck Depression Inventory-II (Beck 1997), Starkstein Apathy Scale (Starkstein et al., 1992), Spielberger State-Trait Anxiety Inventory (Spielberger et al., 1982), Parkinson disease Fatigue Scale (Brown et al., 2005), Parkinson disease quality of life scale (PDQ39) (Peto et al., 1995), and Self-Efficacy (Chen et al., 2011) and Self-Regulation (Schwarzer et al., 1999) scales. Imagery skills will be tested using the Questionnaire on Mental Imagery (Sheehan 1967).

**Hybrid Mental Imagery Practice:** Subjects will practice guided mental imagery of everyday task performance outside the scanner.

**Video-Watching Practice:** Subjects will watch sample video footage of everyday task performance outside the scanner for practice.

**MRI Parameters:** We will conduct the MRI experiments in a Siemens 3.0 Tesla human research

magnet in the MRRC. A 32-channel head coil will be used to collect high-resolution anatomical and echo planar images for fMRI. First, T1-weighted MPRAGE anatomical images (voxel size: 1 x 1 x 1 mm) will be collected for an accurate localization of the fMRI data. Then, axial, T2-weighted, echo planar functional images will be collected (voxel size: 3.5 x 3.5 x 4 mm, 36 slices, FoV: 224 mm, TR: 2000 ms, TE: 25 ms, flip angle: 90°). The number of acquisitions will be 120 (4 min) for each mental imagery and video-watching session.

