**Statistical Analyses:**

Demographic and clinical data: Independent-sample t-tests will be performed to compare the baseline values between the PD-neurofeedback and PD-control groups ( $p < 0.05$ , two-tailed).

**Aim 1:** A 2x2 mixed ANOVA with an interaction term will be performed to assess group differences in right insula-dmFC functional connectivity (between-subject factor: group, within-subject factor: right insula-dmFC functional connectivity during the first and last control scan, interaction: group x insula-dmFC functional connectivity). Post-hoc tests will be Bonferroni-corrected,  $p < 0.05$ .

**Aim 2:** Within-group one-sample t-tests will be performed on the right insula and dmFC resting-state functional connectivity maps. A 2x2 mixed ANOVA with an interaction term will be performed to assess group differences in resting-state functional connectivity (between-subject factor: group, within-subject factor: resting-state functional connectivity pre- and post-intervention, interaction: group x resting-state functional connectivity). All group analyses will be corrected for multiple comparisons using the false discovery rate procedure ( $p < 0.05$ , two-tailed) (Genovese et al., 2002).

**Aim 3:** The scores (i.e., time required for completion) of the motor function tests will be z-transformed and summed to obtain a composite motor function score for each subject. A 2x2 mixed ANOVA will be performed to compare the differences in motor functioning between the groups pre- and post-training (between-subject factor: group, within-subject factors: MDS-UPDRS motor exam and composite motor function scores, interaction: group x motor assessment). Post-hoc tests will be Bonferroni-corrected,  $p < 0.05$ .

**Exploratory Aims:** A paired-sample t-test will be performed to assess the differences in the whole-brain functional connectivity associated with the imagery and video-watching tasks. The results will be corrected for multiple comparisons using the false discovery rate procedure ( $p < 0.05$ , two-tailed) (Genovese et al., 2002).

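### The exploratory rationale asks about equivalence, overlap and a shared imagery network, but the only planned test is for differences, and Exploratory Aim 1 has no second-level test

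*Combined protocol and SAP*

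**What the plan says.** **Rationale for Additional fMRI Experiments (Section I.1).** Two questions justify the new cohort.

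- The first follows from the cited 2022 report that both arms improved. The investigators propose a shared network "subserving both motor and visual imagery and mediating the motor response", and continue: "To test this hypothesis further, we plan on using a hybrid mental imagery of everyday task performance in the scanner".
- The second is to establish "to what extent mental imagery of everyday task performance is equivalent to observation of the actual task performance in terms of brain networks". The interpretation is stated in advance: "If the brain networks involved in these tasks overlap significantly, this will further support the use of mental imagery as a mental training tool".

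**Exploratory Aims 1 and 2 (Section I.1).** The aims are more modest than the rationale. Aim 1 is to examine and measure connectivity during hybrid imagery. Aim 2 is to compare imagining with observing.

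**Research Strategy for the Exploratory Aims (Section I.4, item 3).** Fifteen new subjects each have four 4-minute hybrid-imagery scans and four 4-minute video scans. "All experimental procedures will be completed in one research visit". First-level processing ends with Fisher z-transformed correlation maps for each task.

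**Statistical Analyses (Section 13).** One analysis covers both exploratory aims: "A paired-sample t-test will be performed to assess the differences in the whole-brain functional connectivity associated with the imagery and video-watching tasks". It is FDR-corrected at 0.05, two-tailed. No overlap, similarity, conjunction or equivalence statistic is named, and no margin is given. The power analysis concerns only the main-trial motor score.

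**The concern.** A test for differences answers a different question from the one that motivates the experiment. Significant connections show where the two tasks differ. Non-significant ones show neither equivalence nor overlap. The rationale's criterion of significant overlap therefore has no statistic behind it, and any overlap measure would have to be chosen after the data are in hand.

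The first question fares no better. Imagery against video says nothing about what motor and visual imagery have in common. Exploratory Aim 1 has no second-level test of its own, although main-trial Aim 2 does specify one-sample tests of its connectivity maps.

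At stake is whether the added cohort can answer the questions given for recruiting it.

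**Working it through.** **1. Question against analysis**

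| Question | What would answer it | What is planned |
|---|---|---|
| Which networks serve hybrid imagery (Exploratory Aim 1) | One-sample test of the imagery map | No second-level test |
| Do imagery and observation differ (Exploratory Aim 2 as worded) | Paired t-test | Paired t-test, FDR-corrected |
| How far are they equivalent, do the networks overlap (rationale) | Similarity or conjunction measure, or an equivalence test with a margin | None |
| Is there a shared motor-visual network (rationale) | Separate motor-imagery and visual-imagery conditions | Only hybrid imagery and video in this cohort |
| Does it mediate the motor response (rationale) | Motor outcome measured before and after training | One visit, no repeated motor outcome |

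**2. What a non-significant connection can say at n = 15**

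The documents give no derivation of 15, so there is no planned figure to reproduce. They also give no effect size, SD or margin for this contrast. Results are therefore in units of the SD of the within-subject difference; dz is the mean difference divided by that SD.

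*Precision.* The 95% CI half-width for one connection is t(0.975, 14)/√15 = 2.145/3.873 = 0.55 SD.

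*Power.* This is a two-sided paired t-test with 14 degrees of freedom. Power comes from the noncentral t distribution with noncentrality dz × √15.

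The per-connection alpha implied by FDR control depends on the data. Under the Benjamini-Hochberg procedure the cut-off is about 0.05 times the fraction of connections declared significant. If 20% are declared, it is 0.20 × 0.05 = 0.01; if 2%, it is 0.02 × 0.05 = 0.001. Both fractions are assumptions. Alpha 0.05 is the uncorrected case.

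| Per-connection alpha | dz for 80% power | Missed if true dz = 0.5 | Missed if true dz = 0.8 |
|---|---|---|---|
| 0.05 | 0.78 | 56% | 18% |
| 0.01 (assumed) | 1.00 | 81% | 44% |
| 0.001 (assumed) | 1.32 | 96% | 78% |

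*A formal equivalence test.* Take two one-sided tests at alpha 0.05 on one pre-specified connection, with a true difference of zero. With n = 15, power is 20% for a margin of 0.5 SD and 81% for a margin of 0.8 SD. The margins are assumptions. Fifteen subjects would support equivalence on a single connection only at a margin of about 0.8 SD.

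**3. Is a repair possible with the planned scans?**

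Four runs per task can be split two against two. This gives a within-task similarity against which imagery-video similarity can be judged. It is a ceiling only: the maps are whole-scan correlations, and this cohort has no rest or baseline scan. Some similarity may therefore be task-independent, and no floor is available.

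**The case against.** The strongest defence is that the aims, not the motivating paragraph, define the analysis. Exploratory Aim 2 is to compare, and a paired t-test is the standard way to do so. That stands. The mismatch is between rationale and analysis, and rewording the rationale would remove part of it.

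A reader might infer that the plan intends to read a null result as equivalence. The documents do not say so. The rationale requires networks that overlap significantly, which is a positive though undefined criterion.

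A reader might also infer that few significant differences are to be expected. Nothing supports that either. Watching video and imagining may differ strongly in visual networks. At alpha 0.05 a dz of 0.8 is missed only 18% of the time, and the high miss rates in the table depend on an assumed cut-off.

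The mediation phrase partly interprets an earlier result, and neither exploratory aim claims to test mediation. However, the rationale does say the hybrid task will test the hypothesis further, so the wording needs correcting.

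Finally, the work is labelled exploratory. That excuses the absence of a power calculation. It does not supply a test for the question asked.

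**Conclusion.** The concern holds as a mismatch between the rationale and Section 13. The paired t-test suits Exploratory Aim 2 as worded. It cannot establish equivalence or overlap, and Exploratory Aim 1 has no second-level test. This cohort cannot test the shared motor-visual network or its mediation of motor improvement.

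The type of test is the main defect; the sample size is secondary. Its effect is that a non-significant connection leaves differences of roughly half an SD either side of the estimate unresolved. That figure needs no assumed cut-off. The detectable differences of 1.00 and 1.32 rest on the assumed alphas of 0.01 and 0.001, and all figures are for single connections rather than whole networks.

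The consequence is confined to the exploratory aims. A reader should not infer that the main trial's conclusions are weakened: this is a separate cohort, and none of its data enter the main-trial analyses.

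**What to change.** In Section 13, under Exploratory Aims:

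1. Add FDR-corrected one-sample tests of the hybrid-imagery and video connectivity maps. This gives Exploratory Aim 1 a test.
2. For the overlap question, add a conjunction of the two maps. Add also a per-subject similarity between the imagery and video connectivity matrices, summarised with a 95% CI and set beside the within-task split-half similarity. State that, without a rest or baseline condition, similarity may partly reflect task-independent connectivity. A Dice coefficient should not be the main measure, because it depends on threshold and power.
3. Keep the paired t-test as the difference analysis, and state that non-significance is not evidence of equivalence.

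In the Rationale for Additional fMRI Experiments, tie overlap to the measures in item 2. Remove the claim that this one-visit cohort tests the shared network or its mediation of the motor response.

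Any comparison with the main trial's motor- and visual-imagery control scans should be labelled descriptive and cross-cohort, and should name the scan used (first or last). Those scans come from other subjects and a 40-s block paradigm. Their planned analysis is the right insula-dmFC value, so whole-brain processing would be extra work.

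Items 1 to 3 cost protocol wording and modest extra analysis of scans already planned. No new subjects or scans are needed.

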**Power analysis:** The sample size calculation is based on the clinically important difference (CID) in the primary motor outcome measure. Approximately a 5-point decrease in the mean MDS-UPDRS motor exam score after an intervention has been defined as a moderate CID (Schrag et al., 2006; Shulman et al., 2010). In this study, we expect a moderate CID. We used the mean and standard deviation of the MDS-UPDRS motor exam scores ( $24 \pm 9$ ) of a large group of subjects with PD (N = 347) as the population mean and standard deviation (Shulman et al., 2010). Assuming  $\alpha = 0.05$  and power = 0.80, 22 subjects are required for a moderate CID. Considering the possibility of a 35% drop-out rate between Visits 1 and 4, we will plan to recruit 30 subjects each for the PD-neurofeedback and PD-control group, total of 60 subjects. We will also perform an adaptive interim statistical analysis based on the primary motor outcome (Bauer and Kohne, 1994). If the p values fall between 0.023 (efficacy boundary) and 0.5 (futility boundary), then we will recalculate the sample size based on conditional power (e.g., 0.80). If the p value is  $< 0.023$  (i.e., significant difference) or  $> 0.5$  (i.e., no hope to find a significant difference), we will terminate the study.

**Randomization:** Group assignment of subjects will be determined by the end of Visit 1. We will use a covariate adaptive randomization method (Lin et al., 2015). Age and gender are important variables and need to be controlled during randomization. This method will take into account age and gender and sequentially assign each new subject accordingly. This approach will allow us to balance the two groups in terms of age and gender.

**Potential problems:** 1) Variability in neurofeedback learning will be expected. We aim to reduce variability by providing personalized and detailed motor imagery scripts and facilitate learning with homework. 2) In general, attrition rate can be an issue especially in control groups. Our active control design will help minimize this by controlling for subject engagement in tasks during visits and at home, and for time spent with research staff.

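### The 80% power claimed for 22 subjects per group does not hold for the two-group motor comparison unless an unstated pre-post correlation is about 0.79 or higher (two-sided test)

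*Combined protocol and SAP*

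**What the plan says.** The only sample-size justification is the Power analysis paragraph in Section I, 13. Statistical Considerations. It is built on the primary motor outcome.

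- **Effect:** "5-point decrease in the mean MDS-UPDRS motor exam score after an intervention has been defined as a moderate CID". This describes a change following treatment.
- **SD:** 24 ± 9, a published mean and SD "of a large group of subjects with PD (N = 347) as the population mean and standard deviation". This is the spread of scores between patients.
- **Result:** at alpha 0.05, "power = 0.80, 22 subjects are required for a moderate CID".
- **Recruitment:** "Considering the possibility of a 35% drop-out rate between Visits 1 and 4, we will plan to recruit 30 subjects each", 60 in total.

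The paragraph does not name a test, say whether alpha is one- or two-sided, give an SD of change or a pre-post correlation, or state what change is expected in the control group.

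The comparison being sized is between groups. The Aim 3 hypothesis (Section I, 1. Statement of Purpose) is: "There will be significant improvement in motor function in the PD-neurofeedback compared with the PD-control group post-training". The Aim 3 analysis (Section I, 13) reads: "A 2x2 mixed ANOVA will be performed to compare the differences in motor functioning between the groups pre- and post-training".

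**The concern.** The inputs describe one group measured against a fixed mean, while the trial compares two randomised groups on their change. The two calculations differ in three ways.

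1. A difference between two means has twice the variance of a single mean at the same number per group.
2. The group-by-time test depends on the SD of change. That SD follows from the visit SD of 9 only through a pre-post correlation, which the plan does not give.
3. Five points of improvement in the treated group is a 5-point between-group difference only if controls do not change. The control is active, and the rationale for the additional fMRI experiments (Section I, 1) reports that both groups had comparable motor improvement.

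Readers will take 80% power for a 5-point advantage over control as established, and will read a non-significant result as adequately powered evidence against such an advantage. The stated figure does not support that reading.

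**Working it through.** **Inputs from the plan (Section I, 13).** Difference 5, SD 9, alpha 0.05, power 0.80, 30 recruited per group, 35% drop-out. The standardised difference is d = 5/9 = 0.556.

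**Assumptions.** The plan gives no pre-post correlation ρ, so a range is shown. The SD is 9 at both visits, the true between-group difference in change is 5, and the within-subject factor is pre versus post. With two time points, the interaction F-test is the two-sided two-sample t-test on change. Power is from the noncentral t.

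**Step 1. Is 22 per group or in total?** The text does not say. 22 × 1.35 = 29.7, which rounds to the 30 recruited per group, so I read it as per group. This is the generous reading: 11 per group at SD 9 would give 24% power two-sided.

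**Step 2. Reproduce 22.** Solving for 80% power at d = 5/9:

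| Test | n for 80% power | Power at 22 (per group if two-sample) |
|---|---|---|
| One-sample, one-sided | 21.45 → 22 | 0.809 |
| One-sample, two-sided | 27.4 → 28 | 0.700 |
| Two-sample, one-sided | 40.8 → 41 per group | 0.567 |
| Two-sample, two-sided | 51.8 → 52 per group | 0.437 |

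Only the first row gives 22. That this is where the figure came from is an inference, but it fits the plan's use of the published values "as the population mean and standard deviation".

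**Step 3. The planned comparison.** SD of change = 9 × √(2(1 − ρ)): 12.73 at ρ = 0, 9.00 at 0.5, 6.97 at 0.7 and 5.69 at 0.8.

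Completers if the planned drop-out occurs: 30 × 0.65 = 19.5 per group, fewer than 22. (To retain 22, recruitment would be 22/0.65 = 33.8, so 34 per group.)

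Two-sided power for a 5-point difference in change:

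| ρ | 22 per group | 19.5 per group | 30 per group (no drop-out) |
|---|---|---|---|
| 0 | 0.25 | 0.22 | 0.32 |
| 0.5 | 0.44 | 0.39 | 0.56 |
| 0.7 | 0.64 | 0.59 | 0.78 |
| 0.8 | 0.81 | 0.76 | 0.92 |

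Completers per group needed for 80%: 52 at ρ = 0.5, 42 at 0.6, 32 at 0.7 and 22 at 0.8.

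**Step 4. The correlation that 80% requires.** At 22 per group the SD of change must be at most 5.78, so ρ = 1 − (5.78/9)²/2 = 0.79. At 19.5 per group it must be at most 5.43, so ρ = 0.82. With all 30 per group retained it must be at most 6.80, so ρ = 0.71.

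**Step 5. Difference detectable with 80% power at 19.5 per group.** 8.3 points at ρ = 0.5, 6.4 at 0.7 and 5.2 at 0.8.

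**Step 6. Baseline-adjusted ANCOVA (not planned).** Residual SD = 9 × √(1 − ρ²). Power at 19.5 per group is 0.50, 0.66 and 0.80 at ρ = 0.5, 0.7 and 0.8. Reaching 80% needs ρ of 0.77 at 22 per group and 0.80 at 19.5.

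**The case against.** - **The arithmetic is not wrong, and a high correlation is possible.** 22 is correct for a one-sample, one-sided test. The same scale is scored in the same off-medication state about 4 to 5 weeks apart, so ρ = 0 is unrealistic and nothing in the documents rules out 0.8. This stands. The defect is a mismatch of design plus an unstated assumption, and the trial is not shown to be underpowered at every ρ.
- **Sidedness.** Two-tailed testing is specified for the baseline tests, Aim 2 and the exploratory aims but not for Aim 3, whose hypothesis is directional. One-sided, the required ρ falls to 0.73 at 22 per group, 0.77 at 19.5 and 0.63 at 30. That is fair as a sensitivity range. But the planned interaction F-test is two-sided, and even one-sided the 80% still rests on a ρ that is not stated.
- **Drop-out.** The 35% is worded as a possibility, so 19.5 is a contingency. True, but full retention still needs ρ of about 0.71.
- **Interim analysis.** The plan allows sample-size recalculation when the interim p lies between 0.023 and 0.5, so fixed-sample power is not the trial's overall power. This also stands: any restated figures must be labelled fixed-sample. The rule may raise N, but it does not make the stated figure valid.

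**Conclusion.** The concern holds. On its stated inputs, the 80% power at 22 per group cannot be reproduced for the comparison the trial makes. At SD 9 a two-group test needs 52 per group two-sided or 41 one-sided. On change scores, 80% two-sided requires ρ of about 0.79 at 22 per group and 0.82 at the 19.5 left after the planned drop-out. At 19.5 per group, power is 39% to 76% as ρ runs from 0.5 to 0.8.

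These figures rest on a per-group reading of 22, SD 9 at both visits, a fixed-sample two-sided test and a true between-group difference of 5. If controls improve and the neurofeedback group improves by only the 5 points assumed, the difference is smaller and power is lower. The correction is needed because this is the only justification of sample size.

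**What to change.** Rewrite the power paragraph to:

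1. define the 5 points as a between-group difference in change;
2. name the two-sided group-by-time test, or a baseline-adjusted ANCOVA if that is to become the analysis;
3. state the assumed SD of change or pre-post correlation, with its source;
4. report power at the completers left after drop-out, labelled as fixed-sample and before any interim recalculation.

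Possible wording:

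> For the two-sided group-by-time test (alpha 0.05, SD 9 at each visit), 30 recruited per group with 35% drop-out leave about 19 to 20 completers per group. Fixed-sample power for a 5-point between-group difference in change is about 39%, 59% and 76% at pre-post correlations of 0.5, 0.7 and 0.8. The difference detectable with 80% power is 8.3, 6.4 and 5.2 points respectively.

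If 80% is kept, state and justify the correlation it needs at 19.5 per group: about 0.82 on change scores, or 0.80 with ANCOVA. Because the protocol already reports motor results from groups bearing these names, date the revision and say that it is not prospective.

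**Cost:** protocol and SAP wording only, with no extra patients. The stated power becomes less favourable, or openly conditional on a declared correlation.

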## 2.4. Research Visit 1:

### 2.4.1. Clinical Evaluation:

All subjects will be asked to temporarily hold the morning dose of their dopaminergic medication on Visit 1. Upon obtaining informed consent to participate in the study, [name] will perform an initial physical and neurological examination on all subjects. The diagnosis of idiopathic PD will be made according to the UK Brain Bank diagnostic criteria (Hughes et al., 1992). Cognitive and emotional problems may interfere with imagery performance. To rule out dementia and depression, the Montreal Cognitive Assessment test and Beck Depression Inventory-II will be administered, respectively (Nasreddine et al., 2005; Beck 1997). The Movement Disorders Society-Unified Parkinson’s Disease Rating Scale (MDS-UPDRS) (Goetz et al., 2008) and Hoehn & Yahr staging (Hoehn and Yahr, 1998) are standardized clinical rating scales to determine disease severity and stage in PD. Part III of the MDS-UPDRS is the objective motor examination part that also includes Hoehn & Yahr staging. This part will be videotaped for all subjects. The videos will be viewed and exam features scored by another neurologist with movement disorders training ([name]) who is blind to subjects’ group assignment. The standardized motor function tests (timed up and go, 10-m walking, 2-min endurance walking, five

times sit-to-stand, turning in place 360 degrees, and Physical Performance Test) will be administered to measure movement speed and vigor. All of these are standardized tests and scales, and are commonly used in clinical practice to assess symptom severity in PD.

Immediately after this initial assessment, subjects will take their dopaminergic medication. Subsequently, subjects will be administered additional self-evaluation questionnaires. These include: Starkstein Apathy Scale (Starkstein et al., 1992), Spielberger State-Trait Anxiety Inventory (Spielberger et al., 1982), Parkinson disease Fatigue Scale (Brown et al., 2005), Parkinson disease quality of life scale (PDQ39) (Peto et al., 1995), Self-Assessment Parkinson's Disease Disability Scale (SPDDS) (Biemans, et al., 2001) and Multidimensional Assessment of Interoceptive Awareness (MAIA) questionnaire (Mehling et al, 2012). Motor imagery skills will be tested using the Movement Imagery Questionnaire-3 (MIQ-3) (Williams et al., 2012).

After visit 1, subjects will be randomized to PD-neurofeedback and PD-control groups (see 13. Statistical Considerations).

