#### SECTION VI: RESEARCH ALTERNATIVES AND ECONOMIC CONSIDERATIONS

1. **Alternatives:** What other alternatives are available to the study subjects outside of the research?

Subjects do not receive a specific, standard treatment in this study or forego any treatment in order to participate in this study. The alternative, therefore, is not to participate.

2. **Payments for Participation (Economic Considerations):** Describe any payments that will be made to subjects, the amount and schedule of payments, and the conditions for receiving this compensation.

Subjects will be compensated for their time and receive \$50 for each completed session (maximum total of \$200). The new compensation fee will apply only to new enrollments. The currently enrolled participants will not be affected. Payments will be made electronically through the YCCI Research Subject ePayment program via a prepaid Bank of America card. Subjects' name, address, and telephone number will be shared with Bank of America. On rare occasions, participants may need transportation to the study site and back. We will evaluate this need on a case-by-case basis and provide transportation (e.g., via taxi cab, Uber ride, etc.).

3. **Costs for Participation (Economic Considerations):** Clearly describe the subject's costs associated with participation in the research, and the interventions or procedures of the study that will be provided at no cost to subjects.

Subjects will have to pay for their travel expenses including gas if they drive, or other transportation fees (e.g., bus, train, taxicab). Reimbursement for parking will be provided. Clinical evaluations will be provided at no cost to subjects.

4. **In Case of Injury:** This section is required for any research involving more than minimal risk, and for minimal risk research that presents the potential for physical harm (e.g., research involving blood draws).
  - a. Will medical treatment be available if research-related injury occurs? **Yes.**
  - b. Where and from whom may treatment be obtained? **Treatment may be provided by Yale New Haven Hospital or any health care provider chosen by the subjects.**
  - c. Are there any limits to the treatment being provided? **All necessary treatment will be provided by the treating physician according to standard of care.**

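### Recruiting 30 per group does not preserve the required 22 at the plan's own 35% drop-out: 19–20 remain, and 34 per group would be needed

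*Combined protocol and SAP*

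**What the plan says.** The power analysis in Section I, 13 (Statistical Considerations) starts from a 5-point fall in the MDS-UPDRS motor score, a standard deviation of 9, alpha 0.05 and power 0.80, and concludes that "22 subjects are required for a moderate CID". It does not say whether 22 is per group or in total, which test was used, or whether it was one- or two-sided. It continues: "Considering the possibility of a 35% drop-out rate between Visits 1 and 4, we will plan to recruit 30 subjects each", for a total of 60. No inflation formula is shown.

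Two places fix the timing of allocation. Section 2.4.1 says "After visit 1, subjects will be randomized to PD-neurofeedback and PD-control groups", and the Randomization paragraph of Section 13 says "Group assignment of subjects will be determined by the end of Visit 1". The motor examination is done at Visit 1 and repeated at Visit 4 (Sections 2.4.1 and 2.7.1). The Aim 3 analysis is between groups: "A 2x2 mixed ANOVA will be performed to compare the differences in motor functioning between the groups pre- and post-training".

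Section 13 also has an interim rule. The trial stops if the interim p value is below 0.023 or above 0.5. Otherwise the sample size is recalculated on conditional power.

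**The concern.** A drop-out allowance is meant to leave the required number once the allowed loss has occurred. To leave n after a fraction d is lost, one must recruit n/(1 − d). Recruiting n(1 + d) always leaves fewer than n, because (1 + d)(1 − d) = 1 − d², and at d = 0.35 the gap is no longer negligible.

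The loss in question occurs between Visits 1 and 4. Allocation is settled at about the end of Visit 1, so nearly all of that loss comes out of the randomised groups. A subject lost before Visit 4 has no post-training motor score, and the plan describes neither replacement of drop-outs nor imputation. A reader would take the sentence to mean that 35% attrition leaves the stated 0.80 power intact. On the plan's own figures it does not.

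**Working it through.** **Inputs, all from the power analysis in Section I, 13:** required number 22; drop-out 35%; recruitment 30 per group, 60 in total; difference 5 points; SD 9; alpha 0.05; power 0.80.

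**1. Is the 22 per group?** The unit is not stated. If 22 were a total, inflation would give 30 or 34 in total, not 30 in each group. Only the per-group reading leads to the plan's 60. This is an inference, and the steps below rest on it.

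**2. Reproducing the plan's 30.** Multiplying by 1 + d gives 22 × 1.35 = 29.7, rounded up to 30, which is the stated figure. Dividing by the retained fraction gives 22/0.65 = 33.85, rounded up to 34. That the 30 came from multiplication is inferred from the match; the next step does not depend on it.

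**3. What remains at 35% drop-out.**
- 30 per group: 30 × 0.65 = 19.5, so 19–20 completers, a shortfall of 2–3 against 22.
- 34 per group: 34 × 0.65 = 22.1.

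**4. Drop-out that 30 per group can absorb.** 1 − 22/30 = 8/30 = 26.7%.

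**5. Chance of keeping 22.** Assume each subject drops out independently with probability 0.35.

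| Recruited per group | P(at least 22 complete), one group | Both groups |
|---|---|---|
| 30 | 0.22 | 0.22² ≈ 0.05 |
| 34 | 0.59 | 0.59² ≈ 0.35 |

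Even 34 gives 22 only on average.

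**6. Effect on power.** The documents do not identify the calculation behind the 22. With 5 points, SD 9, alpha 0.05 and power 0.80, two different bases reproduce it:
- a one-sample one-sided t-test (21.45, so 22);
- a two-group two-sided t-test on change scores with a pre–post correlation of 0.8, an assumed value. The SD of change is then 9 × √(2 × (1 − 0.8)) = 5.69, and the number needed is 22 per group.

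Under either basis, power is about 0.81 at 22, 0.77 at 20 and 0.75 at 19.

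The second basis is sensitive to the correlation, which the documents do not give. At 0.7 the same two-group test needs 32 per group. At 0.5 the SD of change is again 9 and it needs 52. At that SD, power is about 0.44 with 22 per group and 0.38–0.40 with 19–20.

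**7. Recruitment totals (secondary).** Section I, 6 says fifty in its text. Section 2.1, the planned enrolment table (18 + 32 + 4 + 6 = 60) and Section 13 say 60. Section III, 1 says 70. The 60 randomised plus the 15 for the exploratory aims (Section I, 4, under item 3 of the research strategy) make 75.

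**The case against.** The case for leaving this alone has several parts.

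- *The consequence is small.* Under both bases that reproduce 22, the loss is about 4–6 percentage points of power. This stands and limits the weight of the point. It remains conditional, because the plan does not say that either basis was used.
- *The binomial figures make 22 look like a cliff.* One completer fewer costs little, and 34 per group also misses 22 fairly often. This is fair. The average shortfall of 2–3 is the useful measure.
- *35% is called a possibility, and the plan never says in words that 22 will remain.* Both are true, and the plan also offers its active control design as a way to limit attrition. But the sentence moves from 22, through 35%, to 30, and has no purpose unless 30 is meant to cover that contingency.
- *30 is not the final size.* Under the interim rule the trial either stops or is resized. This stands, so 30 is a starting figure. The rule acts on the interim p value and conditional power, however, and nothing in it revisits the drop-out allowance.
- *The target of 70 in Section III gives room.* It does not settle the matter. If the 70 includes the 15 exploratory subjects, 70 − 15 = 55 are left for the randomised trial, fewer than 60. If it does not, it contradicts the 60 in Section 13.
- *The basis of the 22 and the enrolment totals are separate matters.* They are. The first is raised only because the power at 19–20 cannot be stated without it; the second is clerical.

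**Conclusion.** The drop-out allowance is wrong as written. If 35% drop out, 30 per group leaves 19–20 completers against the 22 the plan says it needs, a shortfall of 2–3 per group. The plan holds 22 only up to about 27% drop-out, and 34 per group would be needed to expect 22 at 35%.

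This rests on reading 22 as a per-group number of completers, which is the only reading that leads to 30 in each group. It does not depend on how the 30 was obtained. The power cost is probably modest, from about 0.81 to 0.75–0.77 under the two bases that reproduce 22, but it cannot be confirmed until the plan states its basis. For the same reason, 34 per group should not be described as giving 80% power for the between-group Aim 3 comparison. The point should be fixed, but it does not undermine the design. The disagreement among 50, 60, 70 and 75 is a minor clerical matter.

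**What to change.** In the power analysis of Section I, 13:

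1. Replace the drop-out sentence with wording such as: *With 30 subjects per group, 22 completers are retained only if drop-out is at most about 27%. At 35% drop-out, 19–20 per group remain, and the number required for the stated power of 0.80 is not met.*
2. State the basis of the 22: the test, one- or two-sided, per group or total, and whether the SD of 9 is taken as that of scores or of change. Then give the power at 19–20 completers on that basis. No power figure should go in before then.
3. If 22 completers at 35% drop-out is to remain the target, the matching number is 34 per group, 68 in total, described as giving 22 on average.

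Restating the tolerated drop-out is the realistic course. The rationale for the additional fMRI experiments (Section I, 1) already reports that "subjects in both PD-neurofeedback and PD-control groups improved their motor function comparably", and the payments paragraph (Section VI, 2) says of the revised fee that "The currently enrolled participants will not be affected", so enrolment had begun. Items 1 and 2 cost wording only and add no patients; item 3 would add 8 (68 − 60).

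Separately, reconcile the totals of 50, 60 and 70 with 60 + 15 = 75. The documents do not show which total is approved.
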